Self-System Therapy for Older Adults with Advanced Lung Cancer (SST-LC)

NCT04057196

Document Date: May 11, 2020

Purpose of the Study

This pilot project will use Self-system therapy (SST), an empirically validated intervention based to treat depression and lung-cancer-related distress in older adults (65 years and older). We hypothesize that the SST intervention will be both feasible and acceptable. Specifically, lung cancer participants will be successfully recruited to participate in the SST intervention (H1). Participants will complete at least 85% of SST treatment sessions (H2). Participants will report satisfaction with the content and delivery of the intervention, through self-report questionnaires and focus group interviews (H3). Lastly, we hypothesize that participants depression scores will improve from baseline to post-intervention as a function of receiving the SST intervention (H4).

Background & Significance

Older adults diagnosed with advanced lung cancer are highly vulnerable to experiencing symptoms of depression (e.g., sadness; hopelessness) and anxiety (e.g., restlessness; panic; feeling tense). In addition to these symptoms, cancer patients also experience physical symptoms such as chronic pain and breathlessness that lead to sedentary behavior. From a theoretical perspective, having advanced stage lung cancer diagnosis can cause psychological distress because it threatens the individual's own sense of self – particularly, being able to live up to increasingly demanding expectations of their lung cancer care while simultaneously revising and pursuing one's own important personal goals. Faced with these demands, lung cancer patients are prone to self-discrepancies in which they believe that they are failing to meet the expectations that they have for themselves (and that they believe significant others have for them). Older adult lung cancer patients are likely to benefit from learning how to maintain the motivation to pursue important personal goals (e.g., related to emotional and physical health) and how to modify those goals which are not adaptive to their current circumstances. Learning (or relearning) how to set and pursue personal goals that promote growth or accomplishment while modulating or eliminating goals that are unreachable or self-defeating is a key skill for maintaining well-being.

Furthermore, combining this general goal-focused approach with a specific emphasis on becoming more active in the pursuit of quality-of-life-enhancing behaviors would be an ideal match for the needs of these patients and their families. A theory-based, targeted, and readily disseminated intervention for addressing the mental health needs of older adults with advanced lung cancer represents a promising approach to enhancing their psychological and physical well-being.

Design & Procedures

Patients will be recruited from clinics of the Duke Cancer Institute.

Focus Groups or Individual Interviews: We will conduct focus groups (or as needed individual interviews) of older adults with late stage lung in cooperation with Duke's Behavioral Health and Survey Research group (BSHR). These focus group (or as needed individuals) interviews will focus on perceived stresses of everyday living with lung cancer (emotional and physical symptoms), actual-self, ideal-self and ought-self beliefs associated with having an advanced lung cancer diagnosis, self-discrepancy, self-efficacy, stress-related emotions and physiological reactions. Information from the focus groups will be used to

modify the existing evidence-based SST protocols. Each focus group (or individual interview) will be audio-recorded and transcribed for analysis. We will then transcribe the audio recordings and use the grounded theory approach already instantiated in the BHSR's data analytic procedures for qualitative data to identify the main themes and concerns raised by participants.

Creation of a Project Advisory Group of Lung Cancer Patients:

Based focus group (including individual interview) feedback, the project team will identify a subset of who will meet with the project team every four months to receive an updated report on our progress and to solicit ongoing feedback and advice about logistical or other issues that arise during user testing and the pilot trial. Following completion of the focus groups, we will conduct user testing of the developed SST-LC protocol with five older adults with lung cancer. Feedback from user testing will be used to make final revisions to the SST-LC protocol prior to beginning the pilot trial.

[name] is adding a measure to assess the impact of covid on research participants.

Selection of Subjects

Patients will be recruited from clinics of the Duke Cancer Institute. Inclusion/Exclusion criteria are listed below. These will be determined by medical chart review to ensure that participant involvement is appropriate. We are utilizing the duke opt out policy for recruitment purposes.

Inclusion criteria:

- Age \geq 65 years
- English-speaking
- Patient has diagnosis of late stage (III-IV) lung cancer and is living at her/his home.

Exclusion criteria:

- Unable to provide informed consent
- Visual or hearing impairments that preclude participation
- Serious mental illness

On the basis of the patients coming to these oncology clinics and our previous studies with similar populations, we expect that approximately 50% of the sample to be male and 50% female. Based on the ethnic make-up of patients coming to Duke clinics, we anticipate that the ethnic make-up of the entire sample will likely include Caucasian (75%), African-American (15%), Asian (5%) and Hispanic (5%). Recruitment efforts will focus on actively seeking to attract an ethnically diverse sample representative of demographics of the local recruitment area.

Risk/Benefit Assessment

Potential medical risks and discomforts: We do not anticipate any significant medical risks or discomforts to lung cancer patients who consent to participate in the study. Should the health status of

a patient in a way that precludes further study participation, that participant will be able to withdraw from the study as needed (which will be stipulated in the consent form as per Duke University policy).

Potential psychological risks and discomforts: The study is not targeting treatment of psychiatric illnesses, and we do not anticipate that the participants will be at substantial risk of suicidality, self-harm, or harm to others. The PI is a licensed clinical psychologist and works in a research lab that has an in-place, IRB-approved procedure for protection of research participants experiencing acute increases in distress which will be available throughout the duration of this project. All study staff will be trained in this existing procedure (which includes 24-hour phone access to the PI as needed). A situation in which a study participant is at imminent risk of harming him/herself or others may necessitate involuntary reporting and intervention. This risk of loss of confidentiality will be discussed and disclosed to potential participants at the time of consenting. Because psychological interventions for emotional distress invariably require the patient to attend to discomfort and associated thoughts and feeling, participation in the study will be associated with some risk of increased psychological distress, which may include discomfort with attention to unpleasant thoughts, feelings or body sensations. Some individuals may experience an initial increase in undesirable feelings with increased attention to them. SST already contains procedures for identifying, anticipating, and minimizing discomforts that often characterize psychotherapy and related preventive interventions, and the interventionists will be thoroughly trained in how to use those techniques to simultaneously protect participants and assist them in gaining benefit from the intervention. The clinician rating and self-report measures are commonly used for research and clinical purposes. There are no known risks related to their administration, although these assessments may uncover strong and potentially disturbing feelings about the subject's past or present emotional state. In previous studies (spearheaded by co-mentors Drs. [name] and [name]) involving over 1,000 patients, using similar self-report batteries, they have encountered little resultant distress. We will, however, train research staff collecting data to be sensitive to the nature of illness-related issues. When necessary, participants who experience psychological distress related to filling out self-report questionnaires will be referred for appropriate psychiatric or psychological care.

Other risks: The other risks of this study are those associated with confidentiality. In any research project of this type, there is some risk attendant to confidentiality of self-report data. To ensure confidentiality of data, all records will be identified by the participant's identification number, not by name. All raw data will be kept in a locked file cabinet. Protocols and completed measures will be coded by number only, for the purpose of data tabulation and analysis. Data will be stored in protected research computer servers/systems at Duke which employ strict procedures to ensure subject confidentiality. All data will be entered into the computer by study staff only, utilizing code numbers only for subject identification. All information given by the participants will be kept confidential. There will be only one exception to this strict confidentiality policy, which pertains to information obtained during the research assessment which would indicate that the participant is seriously suicidal and may pose a significant and acute risk of self-harm, or if there is a risk of elder abuse. Subjects will be informed of this exception, and will also be informed that such information will be shared with the P.I. of the study and their Attending Physician so that timely and appropriate arrangements for psychiatric assessment and care can be made. This information is included in the Informed Consent form.

Potential Benefits of the Proposed Research to Human Subjects and Others.

There are several potential benefits to study participants. First, participants who receive SST may experience improvements in quality of life, mental health, physical functioning, and self-efficacy. Second, this study will provide data on the feasibility, acceptability, and promise of the new intervention. If study findings suggest that the intervention is feasible, acceptable, and shows promise, we will propose a subsequent, larger multi-site RCT the aims of which will be to test the short- and long-term efficacy of the new intervention on patient outcomes, and on health care utilization. This program of research has the potential to meaningfully enhance the mental health, physical functioning and overall well-being of older adults with late stage lung cancer, change clinical practice, and substantively enhance the quality of life of patients.

Importance of the Knowledge to be Gained.

The risks associated with this study are small compared to the information that will be obtained. The information gathered may lead to major advances in our understanding of how to protect the emotional health physical health of patients with lung cancer. If successful, it may enlarge our repertoire of methods for effectively enhancing the well-being of cancer patients.

Data Analysis & Statistical Considerations

We will use an alpha=5% level of significance to test hypotheses associated with the specific aims. Statistical models will be implemented in statistical software packages (e.g., SAS V9.4 package). Where possible, will use multiple linear regression models (PROC GLM) for continuous outcomes/scales after transforming them to normality, and generalized linear regression models (PROC LOGISTIC, PROC GENMOD) for Likert/ordinal scales and binary outcomes.

For outcomes that are repeatedly assessed throughout the course of the study (e.g., CORE-10), we will use linear mixed-effects regression models implemented in PROC MIXED. All necessary quality-control measures will be implemented to prevent attrition and drop outs to follow-up. All models will be fitted under assumption of MAR utilizing full information likelihood functions, if missing outcomes/covariates are unavoidable.

Evaluating feasibility and acceptability. These measures will be assessed using standard summary statistics and exploratory data analyses.

Initial evaluation of efficacy. Due to small sample size, a simpler model will used instead based on the pre-post difference Likert scales as the dependent variable and use a paired t-test. Specifically, we will compute post-treatment/pretreatment difference scores to assess changes in several outcome measures (that are measured at three time points; distress/CORE-10, depression/BDI, functioning/FACT-L, and physical activity/PASE using simple paired t-tests.

Additional secondary data analysis: We will assess Treatment Quality and Fidelity using evaluations of each VC session by trained raters.

Sample size/power considerations. Sample size of N=30 has been chosen based on effect sizes estimated from previous studies, and after accounting for a 15% attrition rate. We will recruit N=30 older adults, resulting in N=25 effective number of participants. Using the PASS 2015 power program, to attain 80% power at alpha=5% level, we can detect an effect size (Cohen's d) around 0.37 for analyses analyzing pre to post change scores, using paired t-tests, paralleling published findings.ⁱⁱⁱ Similarly, for testing the time effect on the repeatedly assessed distress outcome, we can detect a Cohen's F around 0.50 using a mixed-effects within-subject model with T=12 repeated assessments.

Data & Safety Monitoring

Adverse events will be assessed and fully documented using the standard adverse event forms (including determination of both Adverse Events and Serious Adverse Events as defined by HHS and NIA policies) approved by the Duke University Medical Center IRB and reported to the IRB by the Principal Investigator. For each event, the PI will provide the onset, duration, severity, expectedness, relatedness, outcome and any actions taken. Any related, unanticipated, serious adverse events (i.e., unexpected fatal or life-threatening events related to the study) and severe non-serious adverse events (i.e., requiring therapeutic intervention) will be reported to the IRB and the NIA Project Officer within 24 hours. Any related, unanticipated, moderate or mild adverse events (i.e., alleviated with simple therapeutic treatment or not requiring treatment) will be reported to the IRB and the NIA Project Officer within 3 days.

We do not plan to form a Data and Safety Monitoring Board because this is a Phase I (treatment development) project which will be adapting an existing behavioral intervention. We note that our research team has extensive experience with behavioral interventions in both medically healthy and compromised populations.

We also note that Drs. [name] (PI), [name], and [name] (co-mentors) all are licensed clinical psychologists with active clinical practices and emergency backup. As a team, we will monitor the safety of study participants by doing the following on an ongoing basis:

- Review the research protocol, informed consent documents, and plans for data and safety monitoring.
- Review methodology used to help maintain the confidentiality of study data.
- Review adverse event documentation and make recommendations regarding protection of the safety of study participants.
- Evaluate the progress of the study, including periodic assessments of data quality and timeliness, participant recruitment, accrual and retention, participant risk versus benefit, performance of the study sites, and other factors that may affect study outcome.

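### Do the unlocated focus groups, unnamed satisfaction questionnaire and undefined 85% attendance figure leave H2 and H3 without a usable assessment?

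*Combined protocol and SAP*

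**What the plan says.** The Purpose of the Study lists four hypotheses. H1 concerns successful recruitment. H2 reads "Participants will complete at least 85% of SST treatment sessions (H2". H3 reads "Participants will report satisfaction with the content and delivery of the intervention, through self-report questionnaires and focus group interviews (H3". H4 concerns depression scores.

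Design & Procedures describes one set of focus groups or individual interviews, used to adapt the existing SST protocols. On content: "These focus group (or as needed individuals) interviews will focus on perceived stresses of everyday living with lung cancer (emotional and physical symptoms"; they also cover self-beliefs, self-discrepancy and related reactions. User testing with five older adults comes after the focus groups, and then "Feedback from user testing will be used to make final revisions to the SST-LC protocol prior to beginning the pilot trial". A patient advisory group, identified from the focus-group stage, meets the team every four months to "solicit ongoing feedback and advice about logistical or other issues that arise during user testing and the pilot trial".

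Under Data Analysis & Statistical Considerations, the paragraph on feasibility and acceptability says "These measures will be assessed using standard summary statistics and exploratory data analyses". A separate paragraph on initial efficacy names "distress/CORE-10, depression/BDI, functioning/FACT-L, and physical activity/PASE using simple paired t-tests". The sample size paragraph gives 30 recruited, 15% attrition and 25 effective participants.

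On what follows from the pilot, the Potential Benefits section says "If study findings suggest that the intervention is feasible, acceptable, and shows promise, we will propose a subsequent, larger multi-site RCT".

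**The concern.** Read together, these places seem not to fit. H3 relies on focus groups for satisfaction with the intervention. The only groups described discuss living with the disease, before anyone has received the final SST-LC. User-testing feedback is also spent before the pilot begins. The advisory group does continue, but it gives advice and is not described as a survey of people who were treated. That would leave H3 with questionnaires, and none is identified by name, time point or respondent set.

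H2 has a number but no definition. The 85% could be a mean per person, a pooled share of sessions, or the proportion of people who each reach 85%. It could be taken over everyone who starts or over completers only, and there is no stated rule for people who leave.

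The worry is a choice made after the data are seen. The pilot is meant to inform a larger trial, and the same attendance record could be reported as above or below 85% according to the denominator. Formative feedback might also be presented as satisfaction with treatment.

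**Working it through.** **The plan's own figure.** Inputs from the sample size paragraph: 30 recruited, 15% attrition, 25 effective. 30 × (1 − 0.15) = 25.5, which the plan gives as 25. In reverse, 25 / 0.85 = 29.4, rounded up to 30. The figure reproduces.

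**Can the H2 denominator change the answer?** Assume that all 30 start SST and that the 15% are people who stop sessions; the plan says neither. Let completers attend a fraction c of planned sessions and leavers a fraction p. The completer mean is c. The all-starter mean is 0.85c + 0.15p.

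- c = 0.90, p = 0.25: 0.85 × 0.90 + 0.15 × 0.25 = 0.8025. Completers 90%, all starters 80%: opposite sides of 85%.
- c = 0.95, p = 0.50: 0.85 × 0.95 + 0.15 × 0.50 = 0.8825. Completers 95%, all starters 88%: both pass.

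Setting the all-starter mean to 0.85 gives c = (0.85 − 0.15p) / 0.85. The two readings disagree when c lies from 0.85 to just below this value:

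| Leavers attend (p) | Upper end of c, 15% leavers | Upper end of c, 5 of 30 leave |
|---|---|---|
| 25% | 95.6% | 97% |
| 50% | 91.2% | 92% |
| 75% | 86.8% | 87% |

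The last column uses (25.5 − 5p) / 25. In the extreme case where 5 of 30 leave and attend nothing, even perfect completers give 25/30 = 83.3%.

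So the conflict can arise. The window runs from under 2 percentage points (p = 75%) to about 11 or 12 (p = 25%).

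**Per-person reading.** Sessions needed are 0.85 × S rounded up: 6 of 6, 6 of 7, 9 of 10, 11 of 12, 12 of 13, 12 of 14. The rule allows no missed session in a course of 6 or fewer and one in a course of 7 to 13. The 12 in the sample size paragraph counts repeated distress assessments and is not stated to be a session count, so it does not settle S.

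**H3.** As an illustration, 20 of 25 responders satisfied is 80% (exact 95% CI 59% to 93%), or 20/30 = 67% of starters. H3 sets no threshold, so the choice alters the description but reverses no stated conclusion.

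**Do the passages contradict each other?** H3 does not say that its focus groups are the formative ones. Design & Procedures does not say that those are the only ones. That section gives no session count and no visit schedule for the pilot, so its silence on a post-treatment interview is weak evidence that none is planned. The four scales named for the paired t-tests are efficacy outcomes. They are not an inventory of instruments: acceptability has its own paragraph, and a COVID impact measure is mentioned elsewhere. The sound statement is the narrow one, that no satisfaction scale is named anywhere.

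**Does anything hang on 85%?** The Potential Benefits section makes a larger trial follow from findings of feasibility, acceptability and promise, without a number. The feasibility paragraph plans summaries and describes no test.

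**The case for a change.** The strongest case for a change is that it would cost little: one phrase reconciled in H3, one questionnaire named with its time point, and one definition for H2. The population makes loss likely, since the plan budgets 15% attrition and provides for withdrawal when health declines. The 85% is the only explicit numeric benchmark worded into H1 to H3, although the recruitment target of 30 bears on H1. Fixing the denominator in advance removes a free choice. The analysis section also opens with a general 5% significance level for hypotheses tied to the aims, and the provision for missing data under MAR covers fitted models only, so no stated rule reaches people who leave sessions.

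Much of this stands as description. The text is thin at these points, and a reader of the results would want to know which denominator was used. It does not show that the plan as written yields a wrong result. The specific paragraph on feasibility and acceptability calls for summaries, and attendance can be shown for starters and completers alike. Nor is there one correct definition waiting to be written in. In stage III–IV patients, a mean over all starters that counts sessions after leaving as missed mixes death and progression with acceptability; a completers-only mean hides drop-out. Seeking questionnaires from people who stopped would add contact. Striking focus groups from H3 would discard a useful source if post-treatment interviews are in fact intended. The suggestion that formative feedback would be passed off as satisfaction has no support in the text.

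**Conclusion.** No change to the plan follows. The three omissions are confirmed: no satisfaction interview of pilot participants is described, no satisfaction questionnaire is named, and H2's 85% has no session count, denominator or aggregation rule. They are gaps in description, not stated rules that mislead, and H2 and H3 remain answerable. A competent analyst would tabulate sessions attended out of sessions planned for all who start SST and for completers, with reasons for leaving, and would say which satisfaction instrument was used and who answered it.

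The possible size is limited and conditional. The two H2 readings disagree only when completer attendance falls from 85% to just under 95.6%, 91.2% or 86.8%, for leavers attending 25%, 50% or 75%. This assumes that all 30 start and that the 15% attrition means stopping sessions. With both figures in the report, a disagreement of this kind is visible to the reader, and no stated decision turns on which side of 85% either one falls. The conclusion would differ if the plan made 85% a formal criterion for proceeding to the larger trial; it does not.

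### The detectable Cohen's d of about 0.37 does not follow from the stated inputs: 25 pairs give 0.58 (two-sided) or 0.51 (one-sided) SD of change

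*Combined protocol and SAP*

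**What the plan says.** In the Combined protocol and SAP, Sample size/power considerations justifies the sample size thus: "Sample size of N=30 has been chosen based on effect sizes estimated from previous studies, and after accounting for a 15% attrition rate". It continues: "We will recruit N=30 older adults, resulting in N=25 effective number of participants". Citing PASS 2015, 80% power and 5% alpha, it then gives the detectable Cohen's d as "around 0.37 for analyses analyzing pre to post change scores, using paired t-tests", and says this is in line with published findings.

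The opening of Data Analysis & Statistical Considerations sets the test level: "We will use an alpha=5% level of significance to test hypotheses associated with the specific aims". It does not say one-sided or two-sided. Under Initial evaluation of efficacy, the analysis is "based on the pre-post difference Likert scales as the dependent variable and use a paired t-test", and "we will compute post-treatment/pretreatment difference scores to assess changes in several outcome measures" (CORE-10, BDI, FACT-L and PASE). No SD, standardiser or pre-post correlation is given.

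The hypothesis served by this test is H4 in Purpose of the Study: "Lastly, we hypothesize that participants depression scores will improve from baseline to post-intervention".

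**The concern.** For a paired t-test, the number of pairs, alpha, power and sidedness fix the detectable mean change in units of the SD of change. With 25 pairs that value is well above 0.37 for either sidedness. Reaching 0.37 requires a different standardiser and a pre-post correlation that the plan does not mention.

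This is the only pre-post detectable effect offered in support of N=30. The other figure in the paragraph, a Cohen's F of about 0.50, belongs to a different model with 12 repeated assessments and was not checked here. As written, a reader cannot tell what size of change the H4 test can detect. Someone who believes that power is 80% at 0.37 SD of change could take a null depression result as evidence against an effect of that size. That bears on the next step, described under Potential Benefits: "If study findings suggest that the intervention is feasible, acceptable, and shows promise, we will propose a subsequent, larger multi-site RCT". The stake is limited to H4 and its part in judging promise; H1 to H3 concern feasibility and acceptability.

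**Working it through.** **Inputs.** From Sample size/power considerations: 30 recruited, 15% attrition, 25 evaluable, alpha 0.05, power 0.80, paired t-test. Sidedness is not stated, so both were run.

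**Attrition step.** 30 × 0.85 = 25.5, and 25 / 0.85 = 29.4, which rounds up to 30. This part is consistent.

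**Attempt to reproduce 0.37 on the SD of change.** Let dz = mean change / SD of change. Power comes from the noncentral t distribution with df = n − 1 and noncentrality dz × √n. A normal approximation for n = 25 gives (1.960 + 0.842) / 5 = 0.560 two-sided and (1.645 + 0.842) / 5 = 0.497 one-sided. The exact results are:

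| Pairs | Detectable dz, two-sided / one-sided | Power at dz = 0.37, two-sided / one-sided |
|---|---|---|
| 25 | 0.584 / 0.512 | 42.7% / 56.1% |
| 30 (no attrition) | 0.529 / 0.465 | 50.0% / 63.1% |

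The smallest n with at least 80% power at dz = 0.37 is 60 pairs two-sided (power 80.5%) or 47 one-sided (80.3%). Neither attrition nor sidedness brings the figure near 0.37.

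**Attempt on the raw-score SD.** With equal pre and post SDs and correlation ρ, the SD of change is the raw SD × √(2(1 − ρ)), so raw-SD d = dz × √(2(1 − ρ)). Setting d = 0.37 at n = 25 and solving for ρ:

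- two-sided: ρ = 1 − (0.37 / 0.584)² / 2 = 0.799
- one-sided: ρ = 1 − (0.37 / 0.512)² / 2 = 0.739

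At ρ = 0.80, two-sided: 0.584 × √0.40 = 0.369, which matches the plan's figure. The correlation is an assumption, so the range for n = 25 is:

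| Assumed ρ | Detectable raw-SD d, two-sided / one-sided | Power at raw-SD d = 0.37, two-sided / one-sided |
|---|---|---|
| 0.5 | 0.58 / 0.51 | 42.7% / 56.1% |
| 0.6 | 0.52 / 0.46 | 51.0% / 64.2% |
| 0.7 | 0.45 / 0.40 | 63.0% / 75.0% |
| 0.8 | 0.37 / 0.32 | 80.1% / 88.4% |

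The match at 0.80 does not identify what was done. With 30 pairs, for example, 0.37 is also returned two-sided at ρ = 1 − (0.37 / 0.529)² / 2, about 0.76.

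**What a null result would exclude.** With 25 pairs the 95% confidence interval for the mean change has half-width 2.064 / 5 = 0.413 SD of change. Counting improvement as positive, a two-sided test is non-significant for observed changes from −0.413 to +0.413. The interval excludes an improvement of 0.37 only if the observed change is below 0.37 − 0.413 = −0.043. Most non-significant results on the improvement side would therefore leave 0.37 SD of change open.

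**The case against.** The strongest defence is that nothing was miscalculated. A two-sided test, a d on the raw-score SD and a round correlation of 0.80 return 0.369 and 80.1% power. Cohen's d is used on both scales, and naming the difference score as the dependent variable fixes the test, not the SD used to standardise the effect. The paragraph also refers to earlier studies and carries a reference marker whose entry is not in the available text, so the correlation may come from there. The stakes are modest too: this is a small treatment-development pilot, efficacy is labelled an initial evaluation, no significance threshold for H4 is set for going on to the larger trial, and nothing says that a non-significant result will be read as absence of benefit.

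Much of this stands. A miscalculation is not proven, and the 43% figure applies to one reading only; it should not be quoted as the trial's power. But the defence needs an input that the plan does not contain. The plan cites earlier work for effect sizes, not for a correlation, and its wording ties d to change scores. Even on the favourable reading, the 80% claim falls to 63% at a correlation of 0.7 and 43% at 0.5 (two-sided), so the missing value is not a minor detail.

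**Conclusion.** The concern holds. From the inputs that the plan states, 0.37 cannot be reproduced. On the SD of change the detectable effect is 0.58 two-sided or 0.51 one-sided, with power of 43% or 56% at 0.37. On the raw-score SD the figure is correct only at a pre-post correlation of about 0.80 (two-sided) or 0.74 (one-sided), and at those values there is no shortfall. The documents do not show which of these applies. Reading d as SD of change is the more natural interpretation but remains a judgement, and the raw-SD results assume equal pre and post SDs. The sentence should be corrected because the sample size justification relies on it; the choice of N=30 for a pilot is not in question.

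**What to change.** Keep N=30 and amend Sample size/power considerations as follows.

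- State whether the 5% test is one- or two-sided, and which SD standardises d.
- If d is mean change / SD of change, replace 0.37 with 0.58 (two-sided) or 0.51 (one-sided), and give the power at 0.37 as 43% or 56%.
- If d is on the raw-score SD, keep 0.37 only with the assumed correlation stated and its source given. Show the detectable d (two-sided / one-sided) over a range of correlations: 0.58 / 0.51 at 0.5, 0.45 / 0.40 at 0.7, 0.37 / 0.32 at 0.8.
- Under Initial evaluation of efficacy, commit to reporting the mean change with its 95% confidence interval (half-width about 0.41 SD of change), and to judging from that interval, not from non-significance alone, which effects are excluded.

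The cost is a few lines of protocol text, with no extra participants and the same paired t-test. The drawback is that the stated sensitivity becomes less favourable, or a correlation has to be stated and defended.

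### Does powering the distress outcome at 12 assessments conflict with the three time points listed for CORE-10?

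*Combined protocol and SAP*

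**What the plan says.** Three places in the combined protocol and SAP bear on how often distress is measured.

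- Data Analysis & Statistical Considerations, general methods: "For outcomes that are repeatedly assessed throughout the course of the study (e.g., CORE-10), we will use linear mixed-effects regression models". No number or timing is given.
- Initial evaluation of efficacy: pre-post differences are tested with paired t-tests for four outcomes "that are measured at three time points; distress/CORE-10" and the depression, functioning and physical-activity scales. The small sample is given as the reason for this simpler analysis.
- Sample size/power considerations: after the paired t-test statement, the detectable time effect on the repeatedly assessed distress outcome is put at a Cohen's F "around 0.50 using a mixed-effects within-subject model with T=12 repeated assessments".

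Sessions are mentioned without a count: H2 sets a completion target of 85% of them, and the fidelity analysis uses "evaluations of each VC session by trained raters".

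**The concern.** Read quickly, the plan gives two counts for the same questionnaire. The power sentence does not name CORE-10, but the analysis section identifies distress with CORE-10, and no other distress measure appears. Three and 12 therefore seem to describe one variable, and there is no schedule or session count from which 12 could be derived.

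The count matters for data collection: 25 × 3 = 75 questionnaires against 25 × 12 = 300. It also matters for the model. If time were categorical with an unstructured covariance, the time test would have 2 and 23 degrees of freedom with 6 covariance parameters at three occasions, or 11 and 14 with 78 at twelve. In addition, the power sentence omits the settings needed to check 0.50. If the figure came from the wrong count, the stated sensitivity of the repeated-measures analysis would be unsupported.

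**Working it through.** **The two counts side by side.** The analysis section assigns CORE-10 to a mixed model as a repeatedly assessed outcome, and also to a paired t-test as one of four outcomes with three time points. The power paragraph keeps the same split: a Cohen's d for paired t-tests on change scores, then a Cohen's F for the mixed model on repeatedly assessed distress. Three main assessments with more frequent CORE-10 administration in addition would satisfy all three statements. The documents do not say this outright, but nothing in them excludes it.

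**Inputs for the stated F.**

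- Alpha: 5% ("We will use an alpha=5% level of significance to test hypotheses associated with the specific aims").
- Power: the paired-test sentence says "to attain 80% power at alpha=5% level", and the F sentence continues from it.
- N: "resulting in N=25 effective number of participants". Check: 30 × 0.85 = 25.5, taken as 25.
- T: 12, printed in the power sentence.
- Not given, so assumed here: within-subject correlation ρ from 0 to 0.7, and sphericity correction ε from 1 down to its mathematical floor 1/(T−1) = 1/11.

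**Formula.** For a one-group test of time:

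df1 = (T−1)ε, df2 = (N−1)(T−1)ε, λ = F²·N·T·ε/(1−ρ).

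Find the noncentrality λ that gives 80% power, then F = √[λ(1−ρ)/(N·T·ε)].

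**Can 0.50 be reproduced?** Not from the stated inputs alone, because ρ and ε are needed.

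- ε = 1: df 11 and 264, required λ = 17.43, N·T·ε = 300. At ρ = 0, F = √(17.43/300) = 0.24. At ρ = 0.7, F = √(17.43 × 0.3/300) = 0.13.
- ε = 1/11: df 1 and 24, required λ = 8.53, N·T·ε = 27.27. At ρ = 0, F = √(8.53/27.27) = 0.56. At ρ = 0.2, F = √(8.53 × 0.8/27.27) = 0.50.

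| ε | ρ = 0 | ρ = 0.2 | ρ = 0.5 | ρ = 0.7 |
|---|---|---|---|---|
| 1 | 0.24 | 0.22 | 0.17 | 0.13 |
| 0.5 | 0.30 | 0.27 | 0.22 | 0.17 |
| 0.25 | 0.39 | 0.35 | 0.27 | 0.21 |
| 1/11 | 0.56 | 0.50 | 0.40 | 0.31 |

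So 0.50 is reached at T=12 with ρ = 0.2 and the most conservative correction. It is also reached by a different route: an unstructured covariance (11 and 14 df, required λ = 30.36), AR(1) correlation of 0.7 to 0.8 and a smooth half-cosine trend give 0.505 and 0.503.

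**The case for a change.** The strongest case for acting is that an analyst cannot set up the time factor from this text, and that correction would cost only a few words. It is true that the number and timing of CORE-10 assessments are nowhere stated, that 12 cannot be traced to sessions, and that 0.50 cannot be checked without ρ and the covariance structure. It is also true that the efficacy paragraph could be read as replacing the mixed model with paired t-tests, which would leave the F statement without a test to support.

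What does not stand is the step from a missing schedule to a contradiction. The power sentence prints its count, so there is no doubt about which T it describes. Limiting CORE-10 to three assessments and no more rests on one parenthesis that is never closed. The contrast between 6 and 78 covariance parameters assumes an unstructured model that the plan does not specify; it names only PROC MIXED. If the paired t-tests do replace the mixed model, the F figure carries still less weight. Writing down the schedule and the software settings would improve the record, but it would not alter a result or lead to a better method.

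**Conclusion.** The point does not call for a change. It is a gap in reporting that the study team can fill from its own assessment schedule, and the analyst will fit time at the occasions actually recorded.

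The 0.50 is unverifiable rather than wrong. At N=25 and T=12 the detectable F runs from 0.13 (ρ = 0.7, ε = 1) to 0.56 (ρ = 0, ε = 1/11). These limits rest on assumed values of ρ and ε and on the λ definition shown. In that table 0.50 is at or above every entry except one (ρ = 0, ε = 1/11). For those settings the stated figure claims no more sensitivity than the design has.

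Nothing of consequence depends on it. H4 concerns depression, feasibility and acceptability are summarised descriptively, and no numbered hypothesis uses CORE-10. The plan attributes N=30 to effect sizes from previous studies and to attrition; the F statement only describes what that sample can detect. Settling the count would leave the sample size and the tests of the numbered hypotheses as they are.
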